7SH participants will return their tracking diary to the research assistant during the data collection appointment at 3, 6 and 12-months. Participants will receive a follow-up phone call monthly for the first 3 months, as this is the average time it takes to acquire a new habit. They will then receive a phone call once every 3 months till the end of the intervention period.

Outcome measures:

Primary: (measured at 12-months from intervention commencement)

- Weight change (kg, %) - between group differences

Secondary: (measured at 3, 6, 12 and 24-months from intervention commencement)

- Weight change (kg, %)
- Body Mass Index (BMI)
- Waist circumference (cm)
- Blood pressure
- Health related quality of life, using SF12
- Habit strength
- Self-Regulation of Eating Behaviour
- Fruit and vegetable intake
- Hours of physical activity performed per week
- Temperament
- Number of coach sessions attended (Sum Sanos)
- Number of habits achieved on average per week (7SH-B and 7SH-A)

Other:

Longer time frames for collecting secondary outcome measures (3, 4, 5 years) are dependent on funding.

Participant timeline: See Table 1

-t₁: Eligibility screening over the phone. Study information pack and consent form sent to participant via email. Participant makes appointment time to meet with research assistant.

t₀: Baseline appointment with research assistant. Provide written informed consent and baseline measurements.

t₁: During the baseline appointment, the participant is randomly allocated to an intervention by a member of the research team and informed of their intervention allocation. 7SH participants are given instructions on how to use the booklet or app. Sum Sanos participants are contacted within 24 hours by their assigned Health Coach. Commence intervention.

t₂: 3-month data collection.

t₃: 6-month data collection.

t₄: 12-month data collection. Participants cease intervention. Qualitative interviews.

t₅: 24-month follow-up data collection.

Table 1. Participant timeline

		STUDY PERIOD						
		Enrolment	Allocation	Post-allocation				Follow-up
TIMEPOINT		-t ₁ Screening	t ₀ Baseline	t ₁ Commence intervention	t ₂ 3 months	t ₃ 6 months	t ₄ 12 months	t ₅ 24-months
ENROLMENT	Eligibility screen	x						
	Informed consent		x					
	Allocation		x					
INTERVENTION	Sum Sanos™			←	→	→	→	
	Seven Savvy Habits Booklet			←	→	→	→	
	Seven Savvy Habits App			←	→	→	→	
DATA	Data collection/outcome measurements		x		x	x	x	x

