Participants randomised to Sum Sanos, will be distributed to Life in Balance Pty Ltd (the parent company of Sum Sanos), to assign each participant with a health coach and commence the intervention. Participants randomised to the 7SH-B and 7SH-A groups, will be managed through the central research centre at Bond University.

Blinding: Outcome assessors (research assistants) and data analysts will be blinded to group allocation. Trial participants and the primary investigator will not be blinded to group allocation.

Methods: data collection, management and analysis

Data collection: An experienced research assistant blinded to treatment allocation will be trained by the primary investigator to collect data. The data collection timeline is presented in Table 2.

Table 2. Data collection timeline

	Baseline	3 months	6 months	12 months	24 months	Open-ended
Informed consent	x					
Demographic information	x					
Height	x					
Weight	x	x	x	x	x	x
Waist circumference	x	x	x	x	x	x
Blood pressure	x	x	x	x	x	x
Temperament (24 Q's)	x					
Questionnaires	x	x	x	x	x	x
- Habit-strength (32 Q's)						
- Self-regulation of eating (5 Q's)						
- Effortful Control (19 Q's)						
- Health related quality of life (12 Q's)						
- Fruit and vegetable intake (2 Q's)						
- Exercise behaviours (1 Q)						
Qualitative telephone interview				x		

Anthropometry:

Height will be measured in centimetres using a stadiometer with integrated level. As per NHMRC standard protocol for measuring height ¹; participants will be instructed to stand with feet together and flat on the ground (no footwear), with heels, shoulder blades and buttocks touching the wall. Participants will also be asked to look straight ahead; measurement will be taken as the participant takes a deep breath in and stretch to their fullest height.

Weight will be measured to the nearest 0.1kg using calibrated digital weight scales. As per the NHMRC clinical practice guidelines for the management of overweight and obesity ¹, participants will be asked to remove any outer garments, take off their shoes and empty pockets. Participants will be instructed to stand centred on the scale with weight evenly on both feet.

Body Mass Index will be calculated using body weight in kilograms (kg), divided by height in metres squared (m)².

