Waist circumference (cm) will be measured using a soft tape over light clothing. Measurements will be taken twice and the average of the two recorded. As per NHMRC standard protocol ¹, participants will be asked to remove heavy outer garments, loosen any belts and empty pockets. Participants will stand with their feet close together (about 12-15cm) with their weight equally distributed and breathing normally. Waist is defined as the point midway between the iliac crest and lower rib (approximately in line with the umbilicus). Measurement will be taken in centimetres at the end of normal expiration.

Clinical:

Systolic and diastolic blood pressure will be measured using a calibrated digital inflatable cuff on the upper arm. Whilst seated, participants will be asked to raise their arm to heart level, and rest it on a table, desk or chair. After one to three minutes, the reading will be checked again for accuracy; the average of the two readings will be recorded.

Self-reported questionnaires:

All questionnaires will be distributed to participants via a secure Qualtrics web link. They will complete the questionnaires during their data collection meetings with the research assistant, in a private room at the university or healthcare clinic. Research assistants will inform participants that they may complete the questionnaires at home if they would prefer.

Habit strength: Two questionnaires will be used to measure habit strength.

1. The self-reported, 27-item Creature of Habit Scale (COHS) includes two subscales which incorporate the general concept of habits, namely *routine* behaviour and *automatic* response². The COHS measures individual's propensity for habit in daily life and demonstrates good validity and reliability². Participants rate themselves for each question using a 5-point Likert scale (1. Strongly Disagree, 2. Mildly Disagree, 3. Undecided, 4. Mildly Agree, 5. Strongly Agree), where a higher score reflects a greater expression of habitual behaviours.

2. The strength of habit instigation (deciding to do an action), will be measured using the instigation-specific item of Self-Reported Behavioural Automaticity Index (SRBAI); ('Deciding to do behaviour X is something I do automatically'). The habitual behaviours measured in this research include:
 - Deciding to eat 5 serves of vegetables a day is something I do automatically
 - Deciding to eat 2 serves of fruit a day is something I do automatically

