Statistical methods: Analysis of covariance (ANCOVA) will be used for analysis of pre-post continuous measures collected during the study. For the primary outcome of change in weight at 12 months we will use linear regression to compare change in weight from baseline to 12 months with adjustment for baseline weight. We will use a type 3 analysis of effects to test the null hypothesis of no difference between the 3 treatment groups. If there is evidence of a difference ($P < 0.05$), further pairwise comparisons between groups will be undertaken. Similar analyses will be undertaken for other continuous pre-post outcomes. Treatment effects will be reported as mean differences with 95% confidence intervals.

We plan to finalise and publish a detailed statistical analysis plan (SAP) prior to completion of data collection and before any statistical analysis is undertaken.

Additional analyses: In addition to the primary analysis outlined above we will conduct an adjusted analysis of the primary outcome to assess the impact of any potential baseline imbalances between treatment groups that may have occurred by chance. Variables to be included as covariates for this analysis include treatment site (included as indicator variables), gender and age. BMI will not be included as it is highly correlated with baseline weight which is already included in the ANCOVA regression model.

Handling missing data: We will conduct intention-to-treat analysis. To account for missing primary outcome data, we will implement multiple imputation. In an additional analysis of the primary outcome we will use a per-protocol strategy to compare treatment groups after excluding participants who did not follow the study protocol.

Methods: Monitoring

Harms: Although we do not anticipate harms in this trial, participants are provided with the contact details of the primary investigator prior to recruitment and encouraged to make contact if they experience any harms, discomforts or adverse events. Participants may also discuss harms with the research assistant during data collection appointments. They may also speak with the primary investigator (7SH groups) or health coach (Sum Sanos) during the follow-up calls. An open-ended discussion on consequential events will be discussed during the 12-month interviews.

Ethics and dissemination

Research ethics approval: Ethics approval will be sought from the Bond University Human Research Ethics Committee in Australia.

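### Baseline questionnaires may be completed at home, and nothing requires their receipt before the arm is disclosed, so on one of the protocol's two allocation timings baseline self-report can follow allocation

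*Protocol*

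**What the plan says.** - **Mode and place of completion** (Protocol, Self-reported questionnaires). "All questionnaires will be distributed to participants via a secure Qualtrics web link". The expected place is the visit: "They will complete the questionnaires during their data collection meetings with the research assistant". An alternative is then offered to everyone: "Research assistants will inform participants that they may complete the questionnaires at home if they would prefer". No visit is excepted and no return date is set.
- **Schedule** (Protocol, Table 2). The questionnaire block is marked at baseline and at every later assessment. It covers habit strength, self-regulation of eating, effortful control, SF-12, fruit and vegetable intake and exercise. A separate row, "Temperament (24 Q's", is marked at baseline only; this is the BIS/BAS scale.
- **Timing of allocation, first account** (Protocol, Participant timeline, the t1 entry). The arm is assigned and made known at the first visit: "During the baseline appointment, the participant is randomly allocated to an intervention by a member of the research team". The participant is told the result there and then. For the self-directed arms the entry adds: "7SH participants are given instructions on how to use the booklet or app". Coach contact for Sum Sanos follows within 24 hours, and the entry ends with the start of the intervention.
- **Timing of allocation, second account** (Protocol, Allocation and Implementation). Randomisation follows the baseline assessment and is run one week after recruitment. The primary investigator tells the participant the arm by telephone after a 1-week run-in.
- **Blinding** (Protocol, Blinding). Participants are not blinded.
- **Analysis** (Protocol, Statistical methods). "Analysis of covariance (ANCOVA) will be used for analysis of pre-post continuous measures collected during the study".

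**The concern.** A baseline covariate serves its purpose in ANCOVA only if treatment cannot have influenced it. A questionnaire answered at home after the appointment may be answered by someone who knows the arm and, in the 7SH arms, has already been shown how to use the booklet or app. Some items lie close to what the intervention teaches. The habit-instigation items ask about exercising and everyday activity, and daily activity is one of the 7SH habits that the protocol names. Knowledge of the arm could also colour answers through enthusiasm or disappointment.

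Two uses of these scores are at stake. The first is the between-arm contrasts for the self-reported secondary outcomes. The second is research question 4, which relates temperament to BMI, weight change and other measures, and for which a pre-treatment temperament score is wanted. Neither can be fully repaired at the analysis stage, because a baseline score that was never obtained before allocation cannot be recovered later.

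**Working it through.** The protocol states no figure on this point, so the check is one of sequence, followed by the algebra of the bias.

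**Step 1. Does the home option reach baseline?** The wording covers all questionnaires and names no visit. Table 2 schedules the questionnaires at baseline, so baseline falls within it by wording, although it is not named. BIS/BAS is less certain: Table 2 lists it apart from the questionnaire block, and whether it goes out by the same link has to be inferred.

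**Step 2. Is receipt required before allocation or disclosure?** No sentence says so. The minimisation factors (BMI category, age, gender) do not come from these questionnaires, so randomisation can be run without them. The Implementation paragraph names consent and baseline measurements at the visit and then ties randomisation to elapsed time, not to a received submission.

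**Step 3. Apply each account of timing to a participant who takes the form home.**

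| | Participant timeline (t1) | Allocation and Implementation |
|---|---|---|
| Randomisation | At the baseline appointment | After baseline assessment, one week after recruitment |
| Arm disclosed | At the same appointment | By telephone after the 1-week run-in |
| Baseline form done at home | Always after disclosure, and after 7SH instruction in those arms | Before disclosure if the assessment includes the questionnaires; otherwise after it only when the return takes longer than about a week |

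**Step 4. What a shifted baseline does to the contrast.** With outcome Y, baseline score X and common slope b, the ANCOVA contrast between Sum Sanos (S) and a 7SH arm (H) is

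(mean Y_S − mean Y_H) − b × (mean X_S − mean X_H).

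Suppose a share p in each arm answers late, and that in those participants knowing the arm moves X by d more in S than in H. The expected baseline difference is then p × d instead of 0, and the contrast is off by −b × p × d.

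- If d is positive (enthusiasm in Sum Sanos, disappointment in 7SH), the Sum Sanos advantage is understated on a scale where higher is better.
- If d is negative (for example, 7SH participants score themselves higher after seeing the habits), it is overstated.

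The mechanisms oppose each other and may partly cancel.

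**Step 5. Illustration only.** The documents give none of b, p or d. Assuming b of 0.5 to 0.7, |d| of 0.2 to 0.4 SD and p of 20% to 100%, the absolute bias is:

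- low: 0.5 × 0.2 × 0.2 = 0.02 SD
- middle: 0.7 × 0.5 × 0.4 = 0.14 SD
- bound: 0.7 × 1.0 × 0.4 = 0.28 SD

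The last line needs every participant to answer late, which does not fit a plan whose default is completion at the visit.

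**The case against.** The strongest reply is that the Allocation paragraph already puts randomisation after the baseline assessment. Table 2 lists the questionnaires under baseline, so the natural reading is that the assessment includes them; on that reading no one is randomised before answering. Even on a narrower reading, about a week separates the visit from the telephone call. In addition, completion at the visit is the default, and the timeline lists baseline measurements at t0, ahead of allocation at t1.

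Much of this stands. A reader might infer that the problem remains whichever timing is adopted. The documents do not support that: the second account removes it or confines it to late returns. What the reply does not do is dispose of the t1 entry, which is equally part of the protocol and puts allocation, disclosure and instruction in the baseline appointment. Nor does the protocol define the baseline assessment as including submitted questionnaires.

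Three other inferences also go too far:

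- That the bias always dilutes the treatment effect. Step 4 of the working shows that either sign is possible.
- That every questionnaire score enters an ANCOVA. The statement covers continuous measures taken before and after, and BIS/BAS is collected once.
- That a single shift applies across instruments. General-propensity and temperament scales may well respond less to allocation than items on current behaviour.

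**Conclusion.** The point holds conditionally. If the Participant timeline is followed as written, any participant who uses the home option at baseline gives self-report scores after learning the arm. If the Allocation and Implementation paragraphs are followed, the risk is nil or limited to returns later than about a week, depending on what the baseline assessment comprises. The protocol does not settle which account applies.

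Where it occurs, the self-reported secondary contrasts can be biased in either direction. Effortful control, and BIS/BAS if it is sent by the same link, would no longer be assured pre-treatment predictors. The size cannot be derived from the documents; the 0.02 to 0.28 SD illustration rests wholly on assumed inputs, and its upper end is a bound, not an expectation. A reader might extend the concern to the primary outcome, but baseline weight is measured on scales by the research assistant at the visit, so it is not affected.

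This is more than missing detail that a SAP would supply, because the order of collection is set in the protocol.

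**What to change.** 1. Reconcile the Participant timeline (and the matching columns of Table 1) with the Allocation and Implementation paragraphs, so that the protocol gives one timing for randomisation and disclosure.
2. In the section on self-reported questionnaires, limit the home option to the follow-up assessments, or allow it at baseline only if the form is submitted before randomisation.
3. State that the baseline assessment includes the questionnaires and the BIS/BAS scale, and that MASCoT randomisation is not run until the baseline Qualtrics submission is recorded.

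Item 1 alone is not enough, since neither account makes allocation wait for receipt. How to treat any baseline form that still arrives late can be left to the SAP.

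The cost is a few sentences of protocol text and one check before randomisation. A few participants who prefer to answer at home would be randomised slightly later.

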3. What are the effects of Sum Sanos on fruit and vegetable intake, physical activity levels, blood pressure, waist circumference, health-related quality of life, habit-strength, and self-regulation of eating behaviour at 3, 6, 12 and 24 months, and how do these compare with the 7SH interventions?
4. Is there a relationship between individual temperament and BMI, weight change, habit-strength, health-related quality of life and self-regulation of eating behaviour?
5. What is the relationship between the number of coach-appointments and weight loss?

Objective: The objective of this trial is to assess the effectiveness of a coach-led (Sum Sanos) compared with two self-directed (7SH booklet and app) habit-based interventions on 12-month weight loss outcomes in adults with overweight or obesity.

Hypothesis: We hypothesise that Sum Sanos will be superior for weight loss outcomes compared with 7SH booklet and 7SH app.

Study arms: Sum Sanos vs Seven Savvy Habits Booklet vs Seven Savvy Habits App

Study design: Open-ended, multi-site, 3-armed randomised controlled trial. This is a superiority trial.

Methods: participants, interventions and outcomes

Study setting: This trial will be conducted in the community on the Gold Coast, Australia. Data collection will take place at a Bond University.

Eligibility Criteria: Eligible participants will be aged between 18 and 65 years, have a BMI ≥ 27.0 kg/m², own a smartphone, able to consent for themselves and able to attend all required appointments during the intervention period. Participants will be recruited regardless of obesity-related comorbidities (e.g., cardiovascular disease and diabetes). Exclusion criteria includes participants who are pregnant, significantly ill, participating in other weight management programs, expecting to have bariatric surgery in the next 24-months, or taking medications affecting appetite, metabolism or weight.

Interventions: There are three intervention groups in this trial.

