	Qualitative interviews						x	

Sample size: We aim to observe a difference between Sum Sanos and 7SH intervention groups at 12-months from baseline. Sample size calculations were based on mean weight loss and standard deviation from previous trials using a similar intervention to 7SH. Our power calculation suggests 35 participants are required in each of the 3 arms to achieve a 90% power and 5% significance criterion to detect a 4kg (SD 5.03) difference between Sum Sanos and 7SH intervention groups at 12 months. To account for 30% attrition, we will recruit 138 participants.

Recruitment: The research investigators will recruit participants through local public relations, including newspaper, television and radio advertisement and through social media. Our study timeline has allowed 3 months to recruit the required sample size. The recruitment progress will be monitored on a weekly basis. If the number of enrolled participants is not reaching key milestones, additional public relation outputs will be instigated.

Methods: assignment of interventions

Allocation: Computer generation randomisation will occur after baseline assessment to allocate participants to either Sum Sanos, 7SH-B or 7SH-A (allocation ratio 1:1:1). After a 1-week run-in period, participants will be informed of their study group allocation via telephone by the primary investigator. We will use minimization stratified on, BMI categories (overweight, obese class I, II, III), age (18-30, 31-43, 44-56, 57-65 years); and gender.

Implementation: Individuals interested in participating in the trial will email through their expression of interest using the contact details specified in the media advertisements. The primary investigator will speak with each individual over the phone to conduct initial screening against the eligibility criteria. If eligible, individuals will meet with the research assistant at the relevant university, to provide written consent and baseline measurements. Ineligible individuals will be recommended to see their local health care provider for weight management support.

One week after recruitment to the trial, the primary investigator will randomise participants into one of the three study arms using the clinical trial management software package, MASCoT (<https://mascot.org.au>). Participants will be informed of their allocation via telephone call from the primary investigator.

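### The primary model leaves out the minimisation factors, so its standard errors may be somewhat too large and some available precision is forgone

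*Protocol*

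**What the plan says.** **Allocation (Protocol, Allocation).** "We will use minimization stratified on, BMI categories (overweight, obese class I, II, III), age (18-30, 31-43, 44-56, 57-65 years); and gender".

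**Primary model (Protocol, Statistical methods).** For 12-month weight change, "we will use linear regression to compare change in weight from baseline to 12 months with adjustment for baseline weight". The first test is global: "We will use a type 3 analysis of effects to test the null hypothesis of no difference between the 3 treatment groups". Pairwise comparisons follow if P < 0.05.

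**Additional adjusted analysis (Protocol, Additional analyses).** This is presented as a check on chance baseline imbalance: "Variables to be included as covariates for this analysis include treatment site (included as indicator variables), gender and age". It then adds: "BMI will not be included as it is highly correlated with baseline weight which is already included in the ANCOVA regression model".

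**Sample size (Protocol, Sample size).** 35 per arm "to achieve a 90% power and 5% significance criterion" and "to detect a 4kg (SD 5.03) difference between Sum Sanos and 7SH intervention groups at 12 months". No reduction of the SD for covariates is mentioned.

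The protocol promises a later SAP, but the covariates are already fixed here, and BMI is excluded with a reason. A SAP would have to reverse this text, not merely fill a gap.

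**The concern.** Minimisation makes the arms more alike on BMI class, age and gender than simple randomisation would. To the extent that these factors are prognostic, the difference between arms then varies less from trial to trial. A model that omits them does not register this. It leaves the variation they explain in the residual and computes the standard error as if the factors had been left to chance. The confidence intervals are then wider than the design warrants, and the test rejects less often than 5% under the null.

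At stake are calibration and precision. There is no bias in the treatment estimate and no added false-positive risk. The factors must be known at allocation, so using them in the analysis needs no new data.

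**Working it through.** **Inputs.** From the protocol: difference 4 kg, SD 5.03 kg, 5% significance (two-sided assumed), 90% power, 35 per arm, three arms. Not in the protocol: R², the share of variance in weight change that BMI category, age and gender explain beyond baseline weight. It is assumed here over the range 0 to 0.20.

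**1. The plan's own figure.** The exact two-sample t calculation gives 89.8% power at 34 per arm and 90.6% at 35, so 35 per arm reproduces. It rests on the full SD of 5.03.

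**2. Precision.** Residual SD with the factors in the model is 5.03 × √(1 − R²). The weight-only standard error relative to the adjusted one is therefore 1/√(1 − R²). At R² = 0.10 this is 1/√0.90 = 1.054.

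**3. Calibration with complete follow-up and near-perfect balance.** The true standard error is √(1 − R²) times the reported one. For one comparison the actual two-sided error is 2 × [1 − Φ(1.96/√(1 − R²))]. At R² = 0.10: 1.96/0.949 = 2.066, giving 3.9%. For the three-group test, the large-sample counterpart is 0.05 raised to the power 1/(1 − R²), or 3.6% at R² = 0.10.

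**4. Calibration after 30% random loss.** If balance is achieved at allocation and 70% are then observed, the variance ratio is (1 − R²) + 0.3R² = 1 − 0.7R². Putting √(1 − 0.7R²) into the formula of step 3 gives the fifth column.

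| Assumed R² | Weight-only SE vs adjusted | Type I error, one comparison, complete | Three-group test, complete | One comparison, 30% lost | Pairwise power at 35 per arm, adjusted |
|---|---|---|---|---|---|
| 0 | +0% | 5.0% | 5.0% | 5.0% | 90.6% |
| 0.05 | +2.6% | 4.4% | 4.3% | 4.6% | 92.0% |
| 0.10 | +5.4% | 3.9% | 3.6% | 4.2% | 93.3% |
| 0.15 | +8.5% | 3.4% | 2.9% | 3.8% | 94.5% |
| 0.20 | +11.8% | 2.8% | 2.4% | 3.5% | 95.6% |

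**5. Simulation check.** Three-arm minimisation was simulated with 105 participants, 1,500 runs per R² and assumed covariate distributions, with BMI entered as a continuous variable. Mean standard errors (kg) were:

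| R² | Weight only | + gender, age | + gender, age, BMI |
|---|---|---|---|
| 0 | 1.204 | 1.207 | 1.212 |
| 0.05 | 1.201 | 1.180 | 1.177 |
| 0.10 | 1.206 | 1.162 | 1.148 |
| 0.20 | 1.202 | 1.113 | 1.077 |

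- The ratios of weight-only to full model are 1.201/1.177 = 1.02, 1.206/1.148 = 1.05 and 1.202/1.077 = 1.12, in line with step 2.
- Most of the gain comes from gender and age. Adding BMI after them lowers the standard error by 0.3% at R² = 0.05 and by about 3% at 0.20. This split depends on the simulated covariate effects.
- If the factors predict nothing, adjustment costs 1.212/1.204 = 1.007, or 0.7%.
- At R² = 0.20 the three-group test rejected in 3.2% of null trials with weight only and in 4.9% with all factors. At 0.10 or less, the difference was within simulation error at this number of runs.

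**6. Effect of attrition, simulated.** With 138 minimised and complete follow-up (6,000 runs, Monte Carlo error about 0.3 points), the weight-only three-group test rejected in 4.3%, 3.8% and 3.2% of null trials at R² = 0.05, 0.10 and 0.15. With 30% random loss and completers only, the figures were 5.3%, 4.8% and 4.5%. The planned multiple imputation was not modelled.

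**The case against.** **The effect depends on an unknown.** A reader might infer that the standard errors are certainly too large and that power is certainly lost. The documents do not support that, because they do not say how well the three factors predict weight change beyond baseline weight. At R² = 0 nothing is lost. This objection stands, and the point is conditional on it.

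**Planned power is intact.** A reader might also join this point to the roughly 32 per arm that remain if 30% of 138 are lost (138 × 0.7 / 3 = 32.2), where pairwise power is 87.9%. That shortfall comes from how the sample was inflated for attrition, which is a separate matter. The 35 per arm was computed without covariate credit, and the weight-only model still delivers about 90% there. This objection stands too.

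**Baseline weight is a close proxy for BMI.** The sentence excluding BMI can be read as an argument from redundancy, and the simulation agrees that BMI adds least. That explains why its omission costs little. It is not a reason to bar a factor used in the allocation, since correlation between two baseline covariates does not harm the comparison of arms.

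**Age and gender are already pre-specified in the additional analysis.** They are, and that analysis has a use, since minimisation leaves some imbalance and attrition adds more. But the primary P value and interval do not benefit from it.

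**Site.** From "This trial will be conducted in the community on the Gold Coast, Australia" a reader might infer that the site indicators in the additional analysis are a mistake. The document does not support this. The Study design line describes more than one site, and the introduction and the Implementation, questionnaire and Data management paragraphs also refer to several centres or locations. The protocol is inconsistent about its sites, but that is a different question and does not show an error in this model.

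**Conclusion.** The point holds as a modest, conditional one. The analysis as fixed does not reflect the allocation as fixed: none of the three minimisation factors enters the primary model as such, and BMI enters no planned analysis of the primary outcome.

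If the factors are prognostic beyond baseline weight, the primary analysis is conservative. At an assumed R² of 0.05 to 0.10, the reported standard error is about 3% to 5% larger than it need be. With complete follow-up, the type I error of one comparison is about 4.4% to 3.9%. Attrition partly undoes the balance and brings the error closer to 5%, although the gain in precision from adjustment remains. Relative to the fuller model, about 1.3 to 2.7 points of pairwise power are left unused at 35 per arm (92.0 − 90.6 is 1.3 before rounding; 93.3 − 90.6 = 2.7).

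These sizes rest on the assumed R², a two-sided 5% level, and random loss where attrition is considered. The conclusion is worth acting on because the remedy costs almost nothing, not because the present analysis would mislead.

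**What to change.** - In Statistical methods, define the primary model as 12-month weight change on arm, baseline weight, age (continuous or in the minimisation bands), gender and BMI category.
- Keep the model with baseline weight alone as a sensitivity analysis.
- In Additional analyses, delete the sentence excluding BMI, and revise the covariate list, since age and gender move to the primary model.
- Include the same covariates in the multiple imputation model, so that it matches the analysis model.
- Make the change before any outcome analysis, and carry it into the SAP that the protocol promises.

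**Cost.** Wording only. BMI category (three terms), gender (one) and age (one if continuous, three if banded) use five to seven degrees of freedom, out of about 97 participants if 30% of 138 are lost. If the factors turn out not to be prognostic, the price is a negligible rise in the standard error: 0.7% in the simulation, which used three added terms.
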